
Objective Measures: (a) **Epigenetic (DNAm):** Peripheral blood specimens will be collected at baseline (gestation 12-22 weeks) and intervention week 12 (gestation of 24-34 weeks), as summarized in Table 1. The PD and/or RAs will arrange to meet participants to collect the blood and transport samples to the VCU School of Nursing's lab for DNA extraction.

Samples will be shipped to HudsonAlpha for DNA methylation assays. HudsonAlpha will use the following procedures for DNA methylation: genome-wide methylation patterns will be determined using the 450K HumanMethylation Chip (Illumina) according to the vendor's protocol. Briefly, DNA will be extracted from the blood samples using standard techniques (Puregene Isolation Kit; Qiagen). Following bisulfite conversion of the DNA, the methylation patterns of the 485,764 targets (including CpG islands, shores, open sea) interrogated in the 450K array will be determined. To verify the results of the 450K array for targeted regions of interest, single loci methylation-sensitive studies of bisulfite converted DNA will be conducted using standard methods.²⁰⁵ Gene-specific patterns of candidate genes chosen a priori will be closely examined. All samples will be coded prior to deliver to the testing labs. As methylation patterns vary from tissue to tissue, one concern is if the patterns present in white blood cells are reflective of the relevant cumulative epigenetic changes

involved in chronic depressive symptoms. Skepticism regarding the utility of blood for the assessment of conditions having brain/nervous system components has recently been diminished by the observation that comparable DNAm changes induced by environmental/social events occur in multiple tissues.⁷⁵ Based on these findings, Szyf²⁰⁶ noted that the results of recent investigations demonstrate that it is feasible to study behaviorally related DNA methylation signatures in peripheral cells²⁰⁶ (p.334). Given this supporting data, as well as the practical need to collect a minimally invasive specimen for study in this pregnant population, peripheral blood will be used to assess DNAm patterns. (b) Birth weight: At the postpartum visit, mothers will be asked to report the baby²⁰⁶s birth weight.

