This study will enroll pregnant women who have depression symptoms. Although pregnant women are considered to be a complex or vulnerable population,¹ the National Institutes of Health have stated an objective to encourage research on safe and effective interventions for conditions affecting pregnant women.¹ The self-management intervention is expected to carry less than minimal risk for pregnant participants and no risk to the fetus. No data will be directly collected from the fetus/child; mothers will report the baby's birth weight at the postpartum visit, hence the child is not considered to be a research participant. This study is in compliance with all expectations of research outlined in ²46.46.204 (Additional Protections for Pregnant Women, Human Fetuses and Neonates Involved in Research) of the U.S. Department of Health and Human Services Policy for Protection of Human Research Subjects.²

[name] (PI) has pilot tested the use of a manualized yoga-based PA intervention in a sample of diverse women with moderate-to-severe depressive symptoms; results supported feasibility, acceptability, and short- and long-term

effectiveness.^{18,19,155} We have built upon that study to develop the MOMS intervention by integrating feedback from participants regarding: the length of intervention (we have lengthened the group-based classes from 8 to 12 weeks);¹⁸ and the need for specific knowledge about depressive symptoms and goal-setting to enhance long-term adherence to PA (we have added the nurse-participant partnership and self-guided home PA aspects).¹⁵⁵ We have adapted the group yoga class manual for pregnancy for the MOMS intervention. The PI has recently completed focus groups with pregnant women and new mothers, learning that many women do not receive encouragement from their obstetricians to engage in PA.^{20,137} Moreover, the majority expressed interest in partnering with a healthcare professional to learn about their depressive symptoms and in engaging yoga-based PA as a therapeutic modality for mental and physical well-being.^{20,137} Drs. [name], [name] (Co-I), and [name] (Co-I) have relevant experience with the conduct of randomized controlled trials on health behavior, motivational interviewing, and PA interventions in various populations, including racially and socioeconomically diverse women of child-bearing age, such as those included in this application.¹⁵⁶⁻¹⁵⁹

2. * Select the condition that is applicable to this study [45 CFR 46.204(b)]:

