All study team members will be poised to establish community referrals as needed (e.g. Henrico County Community Services Board: [contact]; Chesterfield County Community Services Board: [contact]; Richmond Behavioral Health Authority: [contact]; local emergency departments).

Protections against risk associated with specimen collection: The risks associated with drawing blood will be minimized by having staff with training in phlebotomy to perform the blood draw.

Protections against risk associated with participant burden: To decrease participant burden, instruments have been chosen that are short and easily self-administered. The blood specimen collection is estimated to take approximately 5 minutes during the appropriate study visits and will be conducted by well-trained personnel.

Protections against risk of physical harm: To minimize risk of physical injury, the prenatal yoga class teachers are certified

to teach yoga modified for pregnancy. Participants will be advised to not participate in yoga if they experience: vaginal bleeding, dizziness, increased shortness of breath, chest pain, new acute headache, muscle weakness, calf pain or swelling, preterm labor/delivery (regular, frequent, painful contractions), decreased fetal movement, or fluid leaking from the vagina, without first consulting with their healthcare provider (per guidelines from the American College of Obstetricians and Gynecologists about when not to exercise in pregnancy).¹² These symptoms are not considered adverse events attributable to yoga but would preclude a participant for engaging in yoga. Our obstetrician collaborator ([name]) will be on call to counsel participants about appropriate treatment options should they experience physical distress.

- 3. If the disclosure of any of the information obtained during the study would place the individual at risk for harm (legal, reputation, emotional etc.) and the information will be recorded so that the individual could be identified, explain the protections that will be put in place to decrease the risk of disclosure:**
- 4. * The Code of Virginia requires that most medical personnel and all employees of institutions of higher education report suspected child/elder abuse or neglect. Is it likely investigators could discover information that would require mandatory reporting by the investigators or staff:**

Yes
 No

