- 8. * Describe criteria for withdrawing an individual participant from the study; such as safety or toxicity concerns, emotional distress, inability to comply with the protocol, etc.:**

We do not anticipate withdrawing a participant from the study, unless she (a) is no longer pregnant due to spontaneous or therapeutic abortion prior to the end of the 12 week intervention period, or (b) she is unable to comply with the protocol and attend a majority of the study sessions, or (c) participant reports any of the following and are advised to cease gentle yoga-based physical activities by their healthcare provider: new vaginal bleeding, new dizziness, new/increased shortness of breath, chest pain, new acute headache, new calf pain/swelling, preterm labor/ delivery (regular, frequent, painful contractions), decreased fetal movement, new fluid leaking from the vagina.

- 9. * Summarize any pre-specified criteria for stopping or changing the study protocol due to safety concerns:**
Participants will be asked to stop engaging in the prenatal yoga classes if they experience any of the symptoms identified by ACOG as reasons to cease physical activity (list in item #8 above). See DSMP.

- 10. Where appropriate, discuss provisions for ensuring necessary medical, professional, or psychological intervention in the event of adverse events to the subjects:**
see data safety monitoring plan

11. * Describe any potential for direct benefits to participants in this study:

We cannot guarantee any direct benefits to participants in the study. The research may yield new knowledge about biobehavioral self-management approaches as adjunctive therapies for perinatal depressive symptoms.

12. * Describe the scientific benefit or importance of the knowledge to be gained:

This study will provide information about the feasibility, acceptability, and preliminary effects of a biobehavioral self-management approach for perinatal depressive symptoms. This line of research will contribute to the body of knowledge about adjunctive therapies for depressive symptoms in pregnancy, a serious problem which contributes to poor maternal-child outcomes. Ultimately, this will contribute to the development and implementation of theoretically driven depression prevention/ resiliency building interventions and measurement of appropriate biobehavioral outcomes to determine the effectiveness of interventions.

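### Item 8 withdraws women from the study, not only the intervention, for low attendance or a provider-ordered yoga stop, so visit 14 and 15 outcomes, including birth weight, can be lost

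*Combined protocol and SAP*

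**What the plan says.** The prompt for item 8 (Risks, Discomforts, Potential Harms and Benefits) concerns withdrawal from the study, and the answer begins "We do not anticipate withdrawing a participant from the study, unless she" and then gives three conditions. Condition (a) is the end of the pregnancy. Condition (b) is that "she is unable to comply with the protocol and attend a majority of the study sessions". Condition (c) is that a "participant reports any of the following and are advised to cease gentle yoga-based physical activities by their healthcare provider", followed by nine symptoms.

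Other places describe a narrower action. Item 9 asks women to stop the yoga classes for "any of the symptoms identified by ACOG as reasons to cease physical activity (list in item #8 above" and refers to the DSMP. The protections against physical harm, under item 2 of the same section, say: "These symptoms are not considered adverse events attributable to yoga but would preclude a participant for engaging in yoga".

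On data collection, Study Visit #14 has the end-of-intervention questionnaires and the second blood sample, and Study Visit #15 has the postpartum questionnaires and interview. The Objective Measures paragraph introduces birth weight with "At the postpartum visit, mothers will be asked to report the baby". The section on Pregnant Women or Fetuses, item 1, repeats that mothers report "birth weight at the postpartum visit, hence the child is not considered to be a research participant".

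The Aim 2 analysis plan keeps the data of women who drop out of the intervention, citing intent-to-treat. For a woman who drops out of the study, the Feasibility and Acceptability Measures paragraph plans an open-ended interview on her reasons and experience.

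**The concern.** Missing most classes and being told by a provider to stop yoga are both reasons to end the intervention. Neither is a reason to stop measuring the woman. Item 8 makes them grounds for leaving the study.

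Three things are at stake.

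- **Birth weight (Aim 2).** Four of the nine 8(c) symptoms are obstetric: bleeding, preterm labor or delivery, decreased fetal movement and fluid leak. If women with these signs leave follow-up, the MOMS mean rests on the less complicated pregnancies. Archival women had no study yoga to stop, so this route to loss does not exist in their groups.
- **Week-12 and postpartum measures (Aims 2 and 3).** 8(b) can remove the later PHQ-9 scores and the second blood sample of the women who attended least. That does not sit well with an intent-to-treat aim.
- **Feasibility (Aim 1).** Adherence and attrition are meant to be separate results. Under 8(b), low adherence becomes attrition by rule.

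**Working it through.** **1. Who meets the rule.** 8(c) needs a listed symptom and provider advice to stop. A woman told to reduce activity but still allowed yoga continues with modified practice (Study Visits #2-#13), so 8(c) covers full stops only. For 8(b), assume that sessions means the 12 classes. A majority is then 7, and a woman stopped medically after 6 or fewer classes meets 8(b) as well as 8(c). If sessions means the 15 contacts, a majority is 8.

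**2. What remains to be collected.** A woman withdrawn during the 12 weeks has visits 14 and 15 ahead of her. Birth weight has no other stated source.

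**3. What the combined document provides after withdrawal.**

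| Provision | Covers | Does not cover |
|---|---|---|
| Aim 2 intent-to-treat sentence | Data of women who leave the intervention | Seeking outcomes not yet collected; women withdrawn from the study |
| Interview after dropout | Reasons and experience | Questionnaires, blood sample, birth weight |
| Mixed linear model | Partly, PHQ-9: earlier scores stay in the model | Birth weight, measured once and correlated with group |
| Survey at 10-20 months | Same measures, women who opted in | The visit 14 and 15 time points; birth weight is not named |

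**4. Size.** The plan gives no figure for item 8 withdrawals. Its only related figure is past attrition of 20-40%, from any cause (Study Population, item 3). On the target of 40, this leaves 40 × 0.80 = 32 or 40 × 0.60 = 24 women, both above the 12 observations cited there. The issue is which women are lost, more than how many.

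The following is an illustration, not an estimate. From the documents: 41 MOMS women and 40 per archival group. Assumed: k MOMS women lost; mean birth weight among them lower by D than among those who stay; SD 500 g.

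Shift in the MOMS mean = (k/41) × D. Standard error of the group difference = 500 × √(1/(41 − k) + 1/40).

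| k (share of 41) | D = 500 g | D = 1000 g | D = 1500 g | Standard error | 1.96 × SE |
|---|---|---|---|---|---|
| 1 (2.4%) | 12.2 g | 24.4 g | 36.6 g | 111.8 g | 219 g |
| 2 (4.9%) | 24.4 g | 48.8 g | 73.2 g | 112.5 g | 221 g |
| 4 (9.8%) | 48.8 g | 97.6 g | 146.3 g | 114.0 g | 223 g |

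Eight of the nine shifts are below one standard error, and all nine are inside the 95% half-width. These shifts assume no similar loss in the archival group.

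**5. Direction.** If j similar women are missing from the archival group, the net shift is D × (k/41 − j/40).

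- j = k: from −0.3 g (k = 1, D = 500 g) to −3.7 g (k = 4, D = 1500 g), practically zero.
- k = 2, j = 4: −25.6, −51.2 and −76.8 g for the three values of D, so the comparison moves against MOMS.

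The documents do not describe archival losses, or whether the 40 per group are chosen from women with complete data.

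**The case against.** The other side has a substantial case.

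- **Unseen documents.** Items 9 and 10 defer to the DSMP, and the Research Description points to an uploaded adverse event protocol. Neither is reproduced in the combined document, and either is a natural place for a follow-up rule. This stands, and the point must be conditional on it.
- **Items 8 and 9 can be read in sequence.** A reader might infer that they contradict each other. They need not: a symptom pauses yoga until the provider is consulted, and only advice to stop triggers 8(c). Item 8 also presents withdrawal as something not expected. This removes the contradiction, but it does not change what 8(c) withdraws her from.
- **Intent-to-treat is stated.** It is, for women who leave the intervention. Retaining data cannot supply a birth weight that was never asked for.
- **The effect is small and this is a pilot.** Feasibility is the primary aim, effectiveness is not being tested, and the plan itself acknowledges the weakness of a non-randomized comparison. Five of the nine 8(c) symptoms are not obstetric (dizziness, shortness of breath, chest pain, headache, calf pain), so deficits of 500 to 1500 g across all women lost are hard to justify. This stands, and it limits the claim about bias. It does not answer the mixing of adherence with attrition, which concerns the primary aim.

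**Conclusion.** The point holds as a flaw in the stated withdrawal rule. As written, 8(b) and 8(c) end study participation for reasons that should end only the intervention, and the combined document has no provision for visit 14 or 15 outcomes afterwards. Any loss would be related to adherence or pregnancy complications. The mixed model covers missing PHQ-9 scores in part; nothing comparable exists for birth weight.

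A reader might go further and infer that these outcomes will be lost, or that the birth weight comparison is materially biased in favor of MOMS. The documents do not support either. Loss is possible, not certain, because the DSMP or adverse event protocol may already require follow-up. The size of any bias cannot be estimated: k, j, D and the SD above are all assumptions. Under them the shift is mostly below one standard error, and its sign depends on archival losses that are not described.

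The change should be made because it is cheap and fits the plan's own intent-to-treat aim. Confidence is medium.

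**What to change.** 1. Reword 8(b) and 8(c): a woman who misses most sessions, or whose provider stops yoga for a listed symptom, discontinues the intervention but stays in the study. She is offered visits 14 and 15 unless she withdraws consent.
2. If visit 15 is missed, ask for the birth weight by phone or email, if she agrees.
3. In Aim 1, report discontinuation of the intervention (medical stops by symptom, and low attendance) separately from study attrition.
4. If the DSMP or adverse event protocol already contains the follow-up rule, cite it in item 8 instead of writing a new one.

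The cost is a change of wording and a few extra contacts with women whom the team already plans to approach after dropout. The sample size does not change.

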**1. * Document Name:**

Consent Form for Follow-Up in person

2. * Type:

Consent/Assent/Information Sheet

3. * File:

R15 extension Consent Form paper %26 pen 4-3-18.pdf(0.05) | History

Add Document

**1. * Document Name:**

Consent Form for Follow-Up Online

2. * Type:

Consent/Assent/Information Sheet

3. * File:

R15 extension Consent Form 4-3-18.pdf(0.05) | History

Add Document

**1. * Document Name:**

Script for Long-Term Follow-Up

2. * Type:

Other

3. * File:

Script for Long-Term Follow-Up 4-3-18.docx(0.03) | History

Add Document

**1. * Document Name:**

Study measures by timepoints

2. * Type:

Research Protocol

3. * File:

Table 1 study measures by timepoints Revised for Amendment 4-3-18.docx(0.02) | History

Add Document

1. * **Document Name:**

Screening Scripts

2. * **Type:**

Research Measure

3. * **File:**

screening_scripts-rev_2-27-17_CLEAN.docx(0.04) | History

ID: MS8_HM20006941

[View: SF_IRB_Summary_Document](#)

Add Document

1. * **Document Name:**

Recruitment Brochure

2. * **Type:**

Recruitment/Advertising

3. * **File:**

brochure rev 10-18-16 to IRB.pdf(0.01) | History

ID: MS8_HM20006941

[View: SF_IRB_Summary_Document](#)

Add Document

1. * **Document Name:**

Consent

2. * **Type:**

Consent/Assent/Information Sheet

3. * **File:**

R15 Consent Form rev 9-7-16 clean.pdf(0.18) | History

ID: MS8_HM20006941

[View: SF_IRB_Summary_Document](#)

Add Document

1. * **Document Name:**

DSMP

2. * **Type:**

Other

3. * **File:**

[name] R15 DSMP revision 9-7-16 clean.docx(0.06) | History

ID: MS8_HM20006941

[View: SF_IRB_Summary_Document](#)

Add Document

1. * **Document Name:**

Protocol for Adverse Event Monitoring

2. * **Type:**

Research Protocol

3. * File:

protocol for adverse event monitoring revision 9-7-16 clean.docx(0.05) | History

ID: MS8_HM20006941

[View: SF_IRB_Summary_Document](#)

Add Document

**1. * Document Name:**

DSMB Approval Letter to Start Study

2. * Type:

Ancillary Committee Approval

3. * File:

DSMB initial meeting letter 8-11-16.docx(0.01) | History

ID: MS8_HM20006941

[View: SF_IRB_Summary_Document](#)

Add Document

**1. * Document Name:**

Recruitment Materials text

2. * Type:

Recruitment/Advertising

3. * File:

Recruitment materials.docx(0.02) | History

ID: MS8_HM20006941

[View: SF_IRB_Summary_Document](#)

Add Document

**1. * Document Name:**

[name] study consent

2. * Type:

Other

3. * File:

HM14000 Consent Form.pdf(0.02) | History

ID: MS8_HM20006941

[View: SF_IRB_Summary_Document](#)

Add Document

**1. * Document Name:**

MINI Psychiatric Interview

2. * Type:

Research Measure

3. * File:

Full MINI v5.0.pdf(0.01) | History

ID: MS8_HM20006941

[View: SF_IRB_Summary_Document](#)

Add Document

1. * **Document Name:**
R15 grant proposal

2. * **Type:**
Funding Proposal

3. * **File:**
Full Proposal without Budget.pdf(0.01) | History

ID: MS8_HM20006941

[View: SF_IRB_Summary_Document](#)

Add Document

1. * **Document Name:**
OSP Internal Doc

2. * **Type:**
Other

3. * **File:**
OSP Internal Review.pdf(0.01) | History

ID: MS8_HM20006941

[View: SF_IRB_Summary_Document](#)

Add Document

1. * **Document Name:**
Study Instruments

2. * **Type:**
Research Measure

3. * **File:**
Study Instruments rev 2-18-16.pdf(0.02) | History

ID: MS8_HM20006941

[View: SF_IRB_Summary_Document](#)

Add Document

1. * **Document Name:**
References

2. * **Type:**
Other

3. * **File:**
[name] R15 Revision References.pdf(0.01) | History

ID: MS8_HM20006941

[View: SF_IRB_Summary_Document](#)

Add Document

1. * Document Name:
Excerpt of Yoga Manual

2. * Type:
Other

3. * File:
[name] R15 Revision Appendix C- Excerpt from Manual for MOMS Intervention revision.pdf(0.01) | History
ID: MS8_HM20006941 View: SF_IRB_Summary_Document

Add Document

1. * Document Name:
Fig 2. Data collection timepoints

2. * Type:
Other

3. * File:
Fig 2 data collection timepoints rev 6-15-15.pptx(0.01) | History

ID: MS8_HM20006941 View: SF_IRB_Summary_Document

Add Document

1. * Document Name:
Study Interview Guides/Scripts

2. * Type:
Research Measure

3. * File:
[name] R15 Revision Appendix B- Interview Guides.pdf(0.01) | History

ID: MS8_HM20006941 View: SF_IRB_Summary_Document

Add Document

1. * Document Name:
Data collection timepoints

2. * Type:
Other

3. * File:
Fig 2 data collection timepoints rev 6-15-15.pptx(0.01) | History

ID: MS8_HM20006941 View: SF_IRB_Summary_Document

Add Document

1. * Document Name:
[name] Biosketch

2. * Type:
CV/Biosketch

3. * File:
[name] R15 Biosketch [name] final.pdf(0.01) | History
